### **9.5.2 Analysis of Secondary Outcomes**

The secondary outcomes listed in Section 9.4.2 have continuous distributions. Accordingly, we will use linear, mixed effects models to explore both between and within-group effects. Longitudinal trends will be investigated for measures such as: in-home body weights, patterns CGM, self-reported daily energy intake, and steps per day. Other important secondary analyses will focus on daily access to the intervention app and trajectories of adherence and engagement in the app as it relates to change in body weight and biomarker endpoints. Residuals will be examined for each outcome and should distributions be deemed not to be normal, appropriate transformations to normality will be sought.

### **9.5.3 Safety Analyses.**

In general, between-group differences in the proportion of participants with AEs will be compared between groups using either chi-square or Exact Tests (when expected cell counts are small). The proportion of participants with other adverse experiences are estimated within intervention groups and expressed as relative effects via risk ratios (95% CIs), or as absolute effects (95% CIs) for between-treatment differences in proportions. Continuous safety measures

will be compared among groups using analysis of variance and 95% CIs. Withdrawals due to SAEs will be summarized by MedDRA code by intervention group.

The exact presentation of analysis results for safety are developed in collaboration with the DSMB. No adjustment for multiplicity is planned for pre-specified safety endpoints.

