## **6 STUDY PROCEDURES**

## 6.1 Schedule of Evaluations

HALLO Pilot Study Measurements	Phone screen	Screening visit 1	Screening visit 2	Baseline visit 1	Baseline visit 2	Intervention	6-month visit	Intervention	9 month visit 1	9 month visit 2
Visit Code	TSI	SV1	SV2	BV1	BV2	INT	FV1	INT	FV2	FV3
Screening & safety assessments										
Phone screen/phone consent	x									
Screening visit: Informed consent/HIPAA form, demographics, CES-D, Montreal Cognitive Assessment (MoCA), Binge Eating Disorder Screener-7, Readiness to change survey		x							CES-D, MoCA	
7-day behavioral and technology run-in			x							
Vital signs (height/weight/BP/pulse/waist circumference)		x					x		x	
Medical history and medications		x								
Blood lipids, HbA1c, CMP, CBC, TSH		x							x	
Extra tube of blood (SST) for instrument QC		x								
DXA body composition (whole body) / bone density (hip, lumbar spine)		x							x	
Medication Updates/Health Status Updates			x	x	x	x #	x	x #	x	x
Siteman cancer online risk assessment & Cancer Screening Questionnaire							x			
Intervention process and adherence measures & feasibility/acceptability										
Total energy expenditure (TEE; doubly-labeled water)				dose / collect urine	collect urine				dose / collect urine	collect urine
Physical activity energy expenditure (PAEE; ActivPAL)				dis-pense	return				dispense	return
Continuous glucose monitoring (CGM)*						x		x		

HALLO Pilot Study Measurements	Phone screen	Screening visit 1	Screening visit 2	Baseline visit 1	Baseline visit 2	Intervention	6-month visit	Intervention	9 month visit 1	9 month visit 2
Questionnaires/Computerized Task: Power of Food Scale; Weight Efficacy Lifestyle Questionnaire; Food Craving Inventory; SF-36; Perceived Stress Scale; PROMIS 13a Fatigue Scale; Pittsburgh Fatigability Scale; Pittsburgh Sleep Quality Index; PROMIS Interest in Sexual Activity; Emotional & Uncontrolled eating; Walking Self-Efficacy; Delayed Discounting, STOP & Epworth Sleepiness questionnaires				x					x	
Night Eating Assessment				x						
Ecological momentary assessments (EMA) of hunger, desire to eat, and anxiety by study Companion App, Fitbit physical activity monitor, Body Trace smart scale^, App-based dietary tracking^						x		x		
Interview: Positive/Negative Outcomes Associated with CR and TRE, Closeout Survey										x
Clinical/biological outcomes										
Resting energy expenditure (REE)				x					x	
Biomarker assays				x			x		x	

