## **9 STATISTICAL CONSIDERATIONS**

### **9.1 General Design Issues**

As suggested by multiple authors (106-108), the design and sample sizes for our HALLO pilot study have been chosen to focus on the feasibility of the design of the targeted full-scale study, rather than on power for hypothesis testing between groups.

During the HALLO pilot, we target the enrollment of approximately 100 participants meeting the inclusion/exclusion criteria to one of three intervention arms 1) 20% CR delivered in-person; 2) 20% CR delivered remotely via video conferencing; and 3) 8-hour TRE with *ad libitum* calorie intake for the first 3 waves (66pts) and the fourth wave will randomize ~24 pp to one of two intervention arms including 20% CR delivered remotely and 8-hour TRE groups. We anticipate randomizing 22:34:34 participants with fewer participants being in the in-person CR group since our group (and others) has more experience with that intervention. From those randomized, we anticipate approximately 20:30:30 participants to complete both pre-and post-measures at 9 months. Data from the enrollment process will be used to refine recruitment criteria, estimate recruitment yields, and test and refine intervention approaches. The pilot will inform three design benchmarks: **a)** The degree of sustained CR (**Benchmark 1**): CR > 10% at 9 months; **b)** TRE sustainability (**Benchmark 2**): At least 75% of participants eating within window on >80% of days; and **c)** **Benchmark 3**: Retention > 85% at 9 months.

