### 9.2.1 Treatment Assignment Procedures

The randomization protocol and the randomization process are prepared and executed by investigators from the Biostatistics and Design Team through the secure web-based data management system, so that eligibility is automatically confirmed, and records are current. The study statisticians have developed the randomization protocol to ensure that sufficient baseline and eligibility data are entered and validated before participants are randomized into the study.

Randomization will be performed stratified on sex, and will use blocked randomizations. Recruitment will target equal numbers of men and women and 23% minority participation. All study personnel, except for the Biostatistics Team will be blinded to the randomization table. We do not anticipate the need to break the randomization code with any urgency, but should it be necessary, it will be decided by the four PIs, with input from the NIH Project Officer. The Study Physician and/or Medical Safety Officer will review descriptions of safety events in an un-blinded manner.

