#### 9.5 Data Analyses

##### 9.5.1 Primary Feasibility Analyses.

Our **primary feasibility outcome (Benchmark 1)** will be absolute rather than relative Energy Intake change to avoid the loss of efficiency and power that has been criticized relative to the direct modeling of ratio measures (110, 111). The primary analyses of DLW-based EI will use constrained mixed linear models (cLDA), with both baseline and follow-up values as model outcomes, to estimate within-group pre-post changes in EI, with group assignment as the primary variable of interest, adjusted for sex (113). We note that the constrained, linear mixed model is extremely flexible, constrains pre-randomization group means to be equal, allows for both intent-to-treat analyses by including participants with incomplete data, and permits inclusion of random effects related to group-based interventions; the traditional ANCOVA can be shown to be one specific parameterization of this model. Kenward et al. (114) note that with proper use of REML

estimation, the constrained, mixed model and ANCOVA are equally efficient (115). Lu (2010) notes that for within group estimation, which is a focus of this pilot study analyses, the ability to include participants with partial data can have advantages relative to reducing bias due to missing data (113).

From these models, the primary finding of interest is whether each group's least squares mean EI one-sided 90% (80%) lower confidence interval excludes the mean value for an average 10% reduction in caloric intake at 9-months based on the mean baseline EI. In addition, using results from this model, we will estimate percent change in EI with a bootstrapped 90% (80%) one-sided confidence interval to provide direct estimates of the relative reduction. Because participants are “grouped” for a component of each intervention, intra-class correlations will be estimated to characterize the dependence of response within intervention groups. Sensitivity analyses will be performed to determine how the width of confidence intervals may depend on the ICC and these analyses will be performed within all randomized groups.

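### Section 9.5.3 compares continuous safety measures by analysis of variance without specifying adjustment for the baseline value or for sex

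*Combined protocol and SAP*

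**What the plan says.** Section 9.5.3 gives continuous safety measures a single clause: they "will be compared among groups using analysis of variance and 95% CIs". It does not say whether the response is the 9-month value or the change, and it names no covariate. It refers to prespecified safety endpoints ("No adjustment for multiplicity is planned for pre-specified safety endpoints") but lists no continuous measure. It adds: "The exact presentation of analysis results for safety are developed in collaboration with the DSMB".

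Other sections bear on the clause:

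- **Stratification.** Section 9.2.1: "Randomization will be performed stratified on sex, and will use blocked randomizations".
- **Data available.** The Section 6.1 schedule lists "Blood lipids, HbA1c, CMP, CBC, TSH" at Screening Visit 1 and at the first 9-month visit. Vital signs and CES-D are also taken at both. Sections 6.2.1 and 6.2.6 agree.
- **Primary model.** Section 9.5.1 uses a constrained longitudinal model with baseline and follow-up values as outcomes, equal pre-randomization means and an adjustment for sex.
- **Secondary outcomes.** Section 9.4.2 lists body weight, fat and lean mass, bone density, muscle mass, and physical and cognitive function. Section 9.5.2 sends these to linear mixed models, though it does not itself name baseline or sex as terms.
- **Numbers.** Section 9.1: "We anticipate randomizing 22:34:34 participants", of whom "we anticipate approximately 20:30:30 participants to complete both pre-and post-measures at 9 months".

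**The concern.** In arms this small, chance differences at baseline are common. An analysis that does not condition on baseline carries part of such a difference into the estimated arm contrast, and it leaves in the residual variation that the baseline value could explain. A real shift in a laboratory value is then harder to see, and a chance gap is easier to mistake for one.

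The unstated response adds to this. Analysis of variance on 9-month values and on change err in opposite directions for the same baseline gap, and the plan leaves the choice open. The document gives no reason for using a simpler method here than for its primary outcome.

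**Working it through.** **The plan's own figures.** The documents state no standard deviation, correlation or interval width for any continuous safety measure, so there is nothing on this point to reproduce. As a check on the completer counts, Benchmark 1 in Section 9.2 follows from 10% of baseline + t(0.90, n−1) × 250/√n:

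- n = 30: 200 + 59.9 = 259.9 kcal/day (stated 260) and 250 + 59.9 = 309.9 (stated 310).
- n = 20: 274.2/2000 = 13.7% and 324.2/2500 = 13.0% (stated 13.7% and 13%).

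**Inputs.** Completers 20:30:30, so N = 80 (Section 9.1). Two-sided 95% intervals (Section 9.5.3). The baseline to 9-month correlation r is an assumption, shown over a range. Sex is given no prognostic effect, because the documents supply none.

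**Formulas.** In units of one SD of the measure, the large-sample standard-error factor is:

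- analysis of variance on the 9-month value: 1
- analysis of variance on change: √(2(1−r))
- ANCOVA: √(1−r²)

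The half-width is t(0.975, df) × factor × √(1/n₁ + 1/n₂). Here df = 77 for analysis of variance and 75 for ANCOVA with baseline and sex.

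**Remote CR against TRE (30 v 30), 95% half-width in SD units:**

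| r | ANOVA, 9-month value | ANOVA, change | ANCOVA | CI narrowing v 9-month value | SE reduction v change |
|---|---|---|---|---|---|
| 0.4 | 0.514 | 0.563 | 0.471 | 8% | 16% |
| 0.5 | 0.514 | 0.514 | 0.445 | 13% | 13% |
| 0.7 | 0.514 | 0.398 | 0.367 | 29% | 8% |
| 0.8 | 0.514 | 0.325 | 0.309 | 40% | 5% |

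The last column is 1 − √((1+r)/2). For in-person CR against either other arm (20 v 30), analysis of variance on 9-month values gives 0.575, and ANCOVA gives 0.498, 0.411 and 0.345 at r = 0.5, 0.7 and 0.8.

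Against analysis of variance on 9-month values, 30 per arm with ANCOVA is worth 30/(1−r²) per arm: about 36, 40, 59 and 83 at the four values of r.

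**Simulation check.** With 1,500 simulated trials at each of r = 0.5, 0.7 and 0.8, mean half-widths were 0.512, 0.512 and 0.510 (9-month value), 0.511, 0.396 and 0.324 (change), and 0.449, 0.370 and 0.311 (ANCOVA). At r = 0.7 the narrowing against 9-month values is 1 − 0.370/0.512 = 28%, so the formulas flatter ANCOVA by only about one percentage point.

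**Chance baseline gap.** The standard error of a difference in baseline means is √(2/30) = 0.26 SD (30 v 30) or √(1/20 + 1/30) = 0.29 SD (20 v 30). A gap above 0.25 SD in either direction therefore has probability 33% or 39%. Given a gap of 0.25 SD, the 9-month contrast shifts by r × 0.25 = 0.125, 0.175 or 0.20 SD at r = 0.5, 0.7 or 0.8. The change contrast shifts by (r−1) × 0.25 = −0.125, −0.075 or −0.05 SD. ANCOVA removes the shift on average.

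**The case against.** The case for leaving the clause alone has several parts.

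- **The pilot is not sized for between-group tests.** Section 9.1 says so, no benchmark in Section 9.4.1 uses a continuous safety contrast, and Section 9.3 has no formal stopping rule. This stands and keeps the point minor. It is not a reason to give up precision that costs nothing.
- **Unadjusted intervals are valid.** Under randomization a chance gap is not bias, and the unadjusted 95% interval already allows for it. This stands. The gap is an error in the single trial, which adjustment reduces.
- **The main harm concerns lie elsewhere.** Bone, muscle and cognition are covered by the mixed models of Section 9.5.2. This stands, and it confines the point to measures outside the secondary list.
- **The DSMB helps settle the safety output.** The text leaves it the presentation of results, which does not clearly extend to the model.
- **Adjustment for baseline and sex does not deal with wave 4**, when allocation dropped to two arms. This is true of contrasts with in-person CR and is a limit of the fix. It applies equally to plain analysis of variance.

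A reader might infer two stronger claims. One is that the plan ignores baseline. The text does not support this, because an analysis of change uses baseline and the response is not stated. The other is that the comparisons are far less precise than the data allow. That would need the 9-month value as response and r of about 0.7 or more, and the documents establish neither.

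**Conclusion.** The point holds as a minor improvement. Section 9.5.3 specifies analysis of variance and leaves out two covariates that are already collected and already used in the primary model. The size depends on two things that the documents do not give: the response and r. Over r = 0.4 to 0.8, the interval would be about 8% to 40% narrower than with 9-month values, or the standard error about 16% down to 5% lower than with change scores. In large samples ANCOVA is no less precise than either, and specifying it closes the open choice of response.

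The benefit of the sex term cannot be quantified from the documents; the case for it is consistency with the stratified design and with Section 9.5.1. The figures assume about 80 completers with both measurements. Naming laboratories, vital signs and CES-D as the measures affected is a reading of the Section 6.1 schedule, since Section 9.5.3 lists none.

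**What to change.** In Section 9.5.3, replace the analysis-of-variance wording with: *Continuous safety measures will be compared among groups by ANCOVA of the 9-month value (or the cLDA model of Section 9.5.1), adjusted for the baseline value of the same measure and sex, with adjusted arm differences and 95% CIs.* The cLDA option has the advantage of keeping participants with partial data. It would help to add a short list of the measures covered.

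The cost is a sentence or two of SAP text. No new data, visits or participants are needed.

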#### **9.5.4. *Other analyses helpful in planning future longer term studies.***

Additional exploratory analyses will use a variety of analytical techniques to examine: (a) the distribution of changes over time in potential outcomes that may be used as part of a composite outcome in the larger study, (b) how adherence characteristics of TRE are associated with weight change, (c) agreement and potential biases between energy intake targets obtained by initially estimating energy intake necessary for a 20% CR through use of DLW versus based upon using REE and an activity level factor specific to sedentary older adults (or based on observed baseline ActivPAL data) (d) associations between actual weights and expected weights based on the trajectory-based model of the relationship of weight loss to energy intake restriction, and factors associated with discrepancies, and (e) measurement properties (e.g., test-retest reliability, variability in time-course within controls) of selected biomarkers (e.g., of IL6, CRP, TNFR1, Cystatin C, insulin levels).

### **10 DATA COLLECTION AND QUALITY ASSURANCE**

#### **10.1 Data Collection Forms**

Data on eligibility, study outcomes and other clinical assessments will be collected by the clinical research staff of the Sticht Center for Health Aging and Alzheimer's Prevention as overseen by the clinical research team. This staff will be blinded to group assignments. Data collection forms can be found in the study MOP. Participant contact information and other PHI will be stored in a secure location that is separate from study data.

#### **10.2 Data Management**

HALLO-P will use the World Wide Web to enter participant data.

**10.2.1 *Clinical Site Responsibilities.*** The single clinical site will maintain appropriate medical and research records for this study, in compliance with federal regulatory and institutional requirements for the protection of confidentiality of participants. The clinical site will also maintain documentation that all members of the research team have completed training requirements. Data collection is the responsibility of the clinical site staff under the supervision of [name], who will be responsible for ensuring the accuracy, completeness, legibility, and timeliness of the data reported.

Data are collected in multiple ways at all participant contacts, including electronic CRFs (**eCRF**) or hard copy CRFs, mHealth app, and automatically generated device data. Clinical site staff are expected to review hard copy CRFs for accuracy and completeness and resolve any data issues prior to data entry. Clinical data (including AEs, concomitant medications) are entered into the website, a 21 CFR Part 11-compliant data capture system. Each clinical site staff member is

authorized before being given a username, password, and staff ID to use the data system on the website.

**10.2.2 Biostatistics and Design Team Responsibilities.** During data entry, a variety of programmed error checks are performed for key variables, such as automatic range checks and logical consistency checks, to identify data that are inconsistent, incomplete, or inaccurate. When these edit checks fail, data may be flagged for further review or prevented from becoming part of the study database. At regular intervals, data queries are carried out on the computerized databases to perform consistency checks on key variables and other data. Metadata of the date, person, programmed edit check results, as well as the creation, modification, deletion, transfer, aggregation, and derivation of data are collected and documented.

Clinical site-generated measurements utilizing instrumentation (e.g., wearable devices measuring activity or glucose levels) will be transmitted to the Data Management Team through Application Programmer Interfaces (APIs). Metadata from these devices is captured and each data type is evaluated for proper storage. Data are archived through the end of the study and/or as required by local and national regulations.

Data security in the web-based data system uses 2048-bit encryption and SSL. Once data are received, recovery from disasters such as natural phenomenon (water, fire, or electrical) is possible through the ability to reconstruct both the database management system and the data up to the last back-up using nightly backups. This process ensures optimal recovery of data systems in the event of a disaster.

Access to the website, privileges to various areas of the website, and to the data on the website is managed by the Biostatistics and Data Management Project Managers in consultation with the clinical site coordinator.

Confidentiality of information is protected through a variety of procedures and facilities:

1. The confidential nature of the data collected, processed, and stored is explained to all new personnel.
2. All access to office space containing data is controlled through a single door, which is locked and only accessible by key or security badge.
3. All participant data are encrypted as described above.
4. All participant data stored on the WFBMC computers are likewise encrypted. In addition, all such databases are protected by passwords that must be supplied before the data can be accessed. Passwords are released only to Biostatistics and Data Management Team staff with a need to use the particular file and are changed on a regular schedule.
5. All printouts, plots, and reports containing individually identifiable data are produced on printers and plotters within the Biostatistics and Data Management Team secure office space.

PHI such as participant name, addresses, contact information and other identifiers of concern, if collected and data entered, are securely stored separately from the main clinical data on eCRFs. Access to these data is limited to a few primary people in the Biostatistics and Design Team and only the PID number connects these data, if required.

Documents pertaining to the study will be maintained for at least until 5 years after the final visit of the last HALLO-P participant.

### **10.3 Quality Assurance**

#### **10.3.1. Training**

Study training will entail didactic and hands-on training. All study staff will be required to read the protocol, the informed consent form and the study manual of procedures. In a series of didactic sessions, the study investigators will explain the rationale of the study, provide an overview of study procedures and measurements, and discuss how to identify and report adverse events. The training will also include a discussion of the ethical conduct of research and the primacy of safety and privacy of study participants. Trainees take a test to make sure the most important training points are retained.

Following this session senior Sticht Center for Health Aging and Alzheimer's prevention staff will demonstrate specific study procedures, ask the staff to practice these procedures, and then observe and certify the examiner on the proper conduct of the measurement and procedure. Study staff will run through practice visits with non-study volunteers to gain experience with each assessment.

The interventionist will be trained under the supervision of [name] and [name].

